### 2.8.3 Vital signs

The summary of vital signs will only include on treatment data, which are defined as those vital sign measurements after the first dose of study treatment and on or before last dose + 84 days.

Analysis in vital sign measurement using descriptive summary statistics for the change from baseline for each post-baseline visit will be performed. These descriptive summaries will be presented by vital sign and treatment group. Change from baseline will only be summarized for subjects with both baseline and post-baseline values and will be calculated as:

change from baseline = post-baseline value – baseline value

The number and percentage of subjects with newly occurring notable vital signs will be presented. Criteria for notable vital sign abnormalities are provided in [Table 2-4](#) below.

**Table 2-4 Criteria for notable vital sign abnormalities**

Vital sign (unit)	Notable abnormalities
Systolic blood pressure (mmHg)	$\geq 140$ mmHg or $< 90$ mmHg
Diastolic blood pressure (mmHg)	$\geq 90$ mmHg or $< 60$ mmHg
Pulse (bpm)	$> 100$ bpm or $< 60$ bpm

## **2.8.4      Electrocardiogram (ECG)**

The summary of ECG will only include on treatment data, which are defined as those ECG measurements after the first dose of study treatment and on or before last dose + 84 days.

The following quantitative variables will be summarized: ventricular rate, RR interval, PR interval, QRS duration, QT interval, and corrected QT interval (QTc). Only Fridericia (QTcF) corrections will be presented for QTc.

QTc will be summarized by computing the number and percentage of subjects (including 95% confidence intervals for pooled analyses, e.g. SCS) with:

[figure not shown]
[figure not shown]
- QTcF > 500 msec
- QTcF > 480 msec
- QTcF > 450 msec
- QTcF changes from baseline > 30 msec
- QTcF changes from baseline > 60 msec

[figure not shown]
PR > 250 msec

[figure not shown]
Summary statistics will be presented for ECG variables by visit and treatment group.

[figure not shown]
[figure not shown]
In addition, shift tables comparing baseline ECG interpretation (normal, abnormal, not available, total) with the worst on-study interpretation (normal, abnormal, not available, total) will be provided.

A listing of all newly occurring or worsening abnormalities will be provided, as well as a by-subject listing of all quantitative ECG parameters.

## 2.12.4 Efficacy Evaluation

### 2.12.4.1 Description of efficacy variables

#### ACR 20/50/70

ACR20 is a binary response variable defined for each subject. A subject will be considered a responder according to ACR20 criteria if he/she has at least (i.e.,  $\geq$ ):

- 20% improvement from baseline in tender 78-joint count
- 20% improvement from baseline in swollen 76-joint count
- 20% improvement from baseline in at least 3 of the following 5 measures:
  - Patient's assessment of PsA pain (VAS 100 mm)
  - Patient's global assessment of disease activity (VAS 100 mm)
  - Physician's global assessment of PsA disease activity (VAS 100 mm)
  - Patient self-assessed disability (Health Assessment Questionnaire [HAQ©] score)
  - Acute phase reactant (C-reactive protein [hsCRP]) or Erythrocyte sedimentation rate (ESR).

In the definition above, the *baseline* value refers to the last measurement made prior to administration of the first dose of study treatment.

The primary endpoint is the proportion of subjects achieving ACR20 at Week 24. Primarily, CRP will be used to calculate ACR response: ESR will only be used in the event CRP is missing.

ACR50 and ACR70 are defined in the same way as ACR20 by replacing the 20% with 50% and 70% improvement from baseline, respectively.

ACRn represents the percent improvement on the continuous scale and from ACRn one can directly calculate ACR20, ACR50, and ACR70 using the appropriate cutoffs. This variable is defined as:

ACRn =  $\min(x_1, x_2, x_3)$ , where

- $x_1$  = % improvement from baseline in tender 78-joint count
- $x_2$  = % improvement from baseline in swollen 76-joint count

and  $x_3$  = 3rd largest value of  $x_4, x_5, x_6, x_7, x_8$  where,

- $x_4$  = % improvement from baseline in Patient's assessment of PsA pain (VAS 100 mm)
- $x_5$  = % improvement from baseline in Patient's global assessment of disease activity (VAS 100 mm)
- $x_6$  = % improvement from baseline in Physician's global assessment of PsA disease activity (VAS 100 mm)
- $x_7$  = % improvement from baseline in Patient self-assessed disability (Health Assessment Questionnaire [HAQ©] score)
- $x_8$  = % improvement from baseline in Acute phase reactant (C-reactive protein [hsCRP]) or Erythrocyte sedimentation rate (ESR)

ACRn can be computed even if up to two values of  $x_4$ ,  $x_5$ ,  $x_6$ ,  $x_7$ ,  $x_8$  are missing. ACRn, theoretically, cannot be computed, if one or both of  $x_1$ ,  $x_2$  is/are missing OR more than three values of  $x_4$ ,  $x_5$ ,  $x_6$ ,  $x_7$ ,  $x_8$  are missing.

### Joint/bone structural damage

The score of primary interest is the total van der Heijde modified Sharpe Score (vdH-mTSS) (van der Heijde 1999), but the erosion score and joint space narrowing score will be analyzed in similar fashion.

#### Derivation of vdH-mTSS

The **total vdH-mTSS** is the sum of scores for erosions and joint space narrowing (JSN) in both hands and feet added together. The erosion and JSN scores are derived as follows:

- **Erosions** will be assessed each hand (20 locations per hand) and each foot (6 locations per foot). The maximum erosion score is 200 for all 40 hand locations, and 120 for all 12 feet locations. Thus, the total possible erosion score is 320. Individual scores range between 0-5 joints of the hands and 0-10 for joints of the feet.
- **Joint space narrowing (JSN)** will be assessed in each hand (20 locations per hand) and each foot (6 locations per foot). The maximum score is 160 for all 40 hand joints, and 48 for all 12 feet joints. Thus, the total possible JSN score is 208. The individual scores of each joint range between 0-4.
- Pencil-in-cup: Osteolysis of the proximal phalanx and the base of the distal phalanx resulting in a pencil like proximal phalanx covered by cup like base of the distal phalanx. Pencil-in-cup will be scored as “P” where applicable.
- Gross Osteolysis: Osteolysis of the phalanx resulting in a loss of the normal joint structure, usually accompanied by shortening of the length of the phalanx. Gross osteolysis will be scored as “G” where applicable.
- If a joint or bone is not visible (e.g. poor film quality, missing imaging, severe misalignment, flexion deformity, dislocation) at the timepoint, the individual joint or bone will be coded as Not Visible (N).
- If radiographs at the timepoint show a joint or bone with surgical fusion, replacement (prosthesis), or amputation, then the joint or bone will be scored Surgically Modified (S).

To obtain the **total vdH-mTSS**, scores for erosions and JSN in both the hands and feet will be added together. Any “P” or “G” will be considered the maximal score for the feature (erosions and JSN) per location in the calculation of the total vdH-S score. Any “N” or “S” will be considered null in the calculation of the total vdH-S score. The range of scores is 0 - 528.

#### Imputation of missing data on joint and segment level:

1. Step - On joint level: The joints are divided into 10 segments according to Table 2-5. In each segment an adequacy threshold is defined. For each segment, when the change from baseline values are available for at least the threshold number of joints, imputation will be applied with the following steps for a given follow-up visit:
  1. The change from baseline will be calculated for the segment and missing joint change from baseline values will be imputed by the within-segment mean change from baseline..

2. Missing baseline and follow-up values will be imputed based on the available data and imputed change from baseline values. If insufficient data is present the mean baseline or mean follow-up value of this segment will be imputed.
3. During the imputation of baseline or post-baseline values implausible values can occur. The following correction step is implemented depending on the value obtained:
  - If a negative value was derived (e.g. for a follow-up visit) this is replaced by 0.
  - If a value greater than the maximum possible score is derived (i.e. >5 for hands and >10 for feet e.g. for the baseline visit) it is replaced by the maximum possible score.

The change from baseline for this joint is updated after this step accordingly.

This algorithm implies that different baseline values can occur for the different follow-up visits if imputation of values is needed.

Otherwise (i.e. if less than threshold number of joints have available change from baseline values), the segment change from baseline will be missing.

2. Step - On segment level: When  $\geq 6$  segments of the 10 segments in total have evaluable change from baseline values, similar as on joint level imputation will be applied with the following steps for a given follow-up visit:
  1. The change from baseline will be calculated across all segments and missing segments change from baseline values will be imputed with the across segments mean change from baseline.
  2. Missing baseline and follow-up values will be imputed based on the available data and imputed change from baseline values. If insufficient data is present the mean baseline or mean follow-up values across segments will be imputed.

Otherwise (i.e. if  $\leq 5$  segments have evaluable change from baseline values), the overall change from baseline value for the segment will be missing.

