6.4.2 Radiographic assessments

Separate radiographs of each hand/wrist (PA) and each foot (AP) will be taken at BSL, Week 16/24, 52, and 104. Bone erosion, joint space narrowing (JSN), and total radiographic scores will be determined using a PsA modified van der Heijde-Sharp (vdH-S) scoring method ([van der Heijde et al 2005](#)) that includes the second through fifth distal interphalangeal (DIP) joints of each hand. Erosions (0–5 in the hands and 0–10 in the feet) and JSN (0–4) will be graded separately in six wrist joints, all metacarpal phalangeal, proximal interphalangeal and DIP joints of each hand, and the first interphalangeal joint and all metatarsal phalangeal joints for each foot. The total radiographic score (hands and feet combined) ranges from 0 to 528, with higher scores indicating more articular damage. The maximum total erosion score is 320. The maximum total JSN score is 208.

The change in the Van der Heijde modified Sharp score is calculated against the BSL value. Radiologists will be trained on the X-ray acquisition and further details will be provided in a manual for the radiologists, e.g. joint placement and beam positioning.

In case of analogue X-rays films, the original film will be sent to the central reading CRO and will undergo quality control and will be digitized. Standard film and cassettes will be provided

[figure not shown]
to all centers that do not produce digital X-rays. In case of digital equipment, sites need to confirm minimum requirements with the imaging CROs. Digital X-rays will be transferred electronically.

In case of insufficient quality, the center will be advised and trained on any quality issues prior to the repeat X-ray and to keep any repeat X-rays to a minimum.

Subjects who are non-responder at Week 16 (not achieving a $\geq 20\%$ improvement from baseline in both TJC and SJC) will have their hands/wrists and feet X-rays taken at this visit (Week 16) and at Week 24 visit. Subjects who are responder at Week 16 ($\geq 20\%$ improvement from baseline in both tender and swollen joint counts) will have their hands/wrists and feet X-rays taken at Week 24.

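### The range correction for imputed joint scores in SAP 2.12.4.1 prints only the erosion limits and omits the joint-space-narrowing maximum of 4

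*SAP*

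**What the plan says.** Under the SAP 2.12.4.1 heading on imputation at joint and segment level, "The joints are divided into 10 segments according to Table 2-5". Table 2-5 lists five erosion segments and five JSN segments. Where enough joints in a segment have a change score, "missing joint change from baseline values will be imputed by the within-segment mean change from baseline", and the missing baseline or follow-up value is rebuilt from that change.

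A correction follows for implausible results. Negative values become 0. For a value that is too high, the limit is given in a bracket, "i.e. >5 for hands and >10 for feet e.g. for the baseline visit", and "it is replaced by the maximum possible score". The joint's change from baseline is updated after this step. No separate limit for JSN is given.

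The preceding part of the same section defines the scales. For erosions: "Individual scores range between 0-5 joints of the hands and 0-10 for joints of the feet". For JSN: "The individual scores of each joint range between 0-4", and "Thus, the total possible JSN score is 208". Protocol 6.4.2 gives the same 0 to 4 range for JSN and agrees on the total: "The maximum total JSN score is 208".

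**The concern.** The correction covers both features, but the only numbers in it belong to erosions. A programmer who works from those numbers will leave JSN values between 4 and 5 in the hands, and any imputed JSN value in the feet, as they are. The change score for that joint is then also wrong, because it is updated only if the correction fires.

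The derived quantity is the change in vdH-mTSS, which sits in the first hypothesis family and drives the sample size. The JSN score is also analysed in its own right, and the same change score is cut at 0.5 for the no-structural-progression endpoint.

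The affected joints are not far-fetched. A joint may be coded as not visible for severe misalignment, flexion deformity or dislocation, and such a joint may well be close to the top of the JSN scale. That last step is an inference; the documents give no frequency.

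**Working it through.** **1. The plan's own maxima.** SAP 2.12.4.1 and Table 2-5 give 40 hand and 12 foot locations per feature.
- Erosion: 40 × 5 + 12 × 10 = 320.
- JSN: 40 × 4 + 12 × 4 = 208.
- Total: 320 + 208 = 528.

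All three agree with the SAP and with protocol 6.4.2. They require a JSN maximum of 4 in every joint.

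**2. When an imputed JSN value passes 4.** Let m be the segment mean change.
- Missing follow-up: imputed follow-up = baseline + m. This exceeds 4 if m > 0 and baseline > 4 − m.
- Missing baseline: imputed baseline = follow-up − m. This exceeds 4 if m < 0 and follow-up > 4 − |m|.

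For a joint exactly at 4 the uncorrected excess is |m|, up to the printed cap.

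**3. Examples, printed limits against a JSN cap of 4.**

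| Case | m | Imputed value, printed | Change, printed | Change, cap 4 |
|---|---|---|---|---|
| Single joint, follow-up 4, baseline missing | -0.5 | 4.5 | -0.5 (joint) | 0 (joint) |
| Hand PIP segment: one joint at baseline 4, follow-up missing; one of 7 observed joints worsens by 1 | 1/7 = 0.143 | 4.143 | 1.143 (segment) | 1.000 (segment) |
| Foot segment: one joint at baseline 4, follow-up missing; 11 observed joints change by 3 in total | 3/11 = 0.273 | 4.273 | 3.273 (segment) | 3.000 (segment) |

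None of these values exceeds 5 in the hands or 10 in the feet, so the printed trigger does not fire. Reading only the replacement value as 4 changes nothing here.

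**4. Upper bounds.**
- Hand: the value is left or capped at no more than 5, so the excess is at most 5 − 4 = 1.
- Foot: the largest imputable value is 4 + 4 = 8, so the limit of 10 never binds and the excess is at most 8 − 4 = 4. That needs every observed foot joint to move from 0 to 4.
- Per reader, subject and visit: the adequacy thresholds in Table 2-5 allow (8 − 5) + (8 − 5) + (12 − 7) + (12 − 7) = 16 hand and 12 − 7 = 5 foot JSN joints to be imputed. The arithmetic ceiling is 16 × 1 + 5 × 4 = 36 points. This is a bound, not an expectation.

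**5. Effect on the 0.5 cut-off.** Take the PIP example. Assume two readers and no third read, no change according to the second reader, and no change in the other segments for either.
- Printed: (1.143 + 0)/2 = 0.571, which is above 0.5, so the subject counts as a progressor.
- Cap 4: (1.000 + 0)/2 = 0.500, which is not above 0.5, so the subject counts as a non-progressor.

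**6. Later steps.** The cap in SAP 4.2.7.1 acts on the linearly extrapolated Week 24 score and does not correct a single joint. The SAP also says that no further imputation follows during the analysis.

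**7. Power.** A Satterthwaite t-test with SDs 1.132 and 2.435, difference 0.52, 220 against 330 subjects and two-sided alpha 0.05/3 gives 83.3%, which reproduces the stated 83%. The capping rule does not enter this calculation.

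**The case against.** The strongest reply is that the rule is generic. It refers to the highest score that can occur, and the scale definitions just above it make that 4 for JSN. The rule for pencil-in-cup and gross osteolysis codes already uses a maximum specific to feature and location. On this reading the bracket is merely incomplete.

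This stands in part. A reader might infer that the SAP deliberately caps JSN at 5 and 10; it does not say so, and the intent was probably 4. But the bracket is introduced as a definition of the limit, with a separate marker for its illustration, and it holds the only numbers in the step. Section 2.12.4.1 also refers to an appendix for each reader's total score. That appendix is not in the text available, so whether it gives limits by feature cannot be checked.

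Other parts of the reply also stand:
- The -0.5 example is large. Over the minimum of five observed joints in an eight-joint segment it means 5 × 0.5 = 2.5 points of improvement, against an assumed placebo SD of 2.435 for the whole score. The 0.143 case is more ordinary.
- Averaging over two or three readers shrinks the excess further if only one reader lacks the joint.
- A reader might take the foot excess to be 10 − 4 = 6. The algorithm cannot produce it, as step 4 shows.
- A reader might expect JSN totals above 208. That would need virtually all 52 JSN locations at their maximum, which is practically out of reach.

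**Conclusion.** The correction step is wrong as printed for JSN: its numeric limits fit erosions only and conflict with the 0 to 4 JSN range in the same section and in the protocol. The consequence is conditional. The bracket must be programmed literally, and a JSN joint at or near 4 must lack a baseline or follow-up reading. The excess is then at most 1 point per hand joint and 4 per foot joint, typically a fraction of a point.

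A reader might infer that the treatment comparison is biased. The documents do not support that: the rule is identical in all arms, readers are blinded to treatment and film sequence, and the frequency of the situation is not given. The effect on the assumed difference of 0.52 therefore cannot be computed; it is probably small. What remains is a wrong joint score and change for the affected subjects, and possible misclassification at the 0.5 cut-off. This is a minor point, worth correcting because the correction is so cheap.

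**What to change.** Replace the bracket with limits by feature, for both the trigger and the replacement value: erosion 5 (hands) and 10 (feet); JSN 4 (hands and feet). Keep the existing instruction to update the joint's change after capping. Check the derivation program against this wording.

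The segment-level step is described as similar to the joint-level one but lists no range correction; the same edit can state whether segment bounds apply.

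Cost: one clause in the SAP and a short program check. No data collection, sample size or test is affected.

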**Table 2-5 Segmental distribution**

Segment	Total number of joints	Adequacy threshold	Joints at one side	Location of joints
PIP erosions	8	5	PIP2, PIP3, PIP4, PIP5	Hand
DIP erosions	8	5	DIP2, DIP3, DIP4, DIP5	Hand
MCP + thumb erosions	12	7	MCP1, MCP2, MCP3, MCP4, MCP5, INTERPHALANGEAL JOINT OF THE HAND	Hand
Wrist erosions	12	7	FIRST METACARPAL BONE, DISTAL RADIUS, DISTAL ULNA, TRAPEZOID-TRAPEZIUM, NAVICULAR BONE, LUNATE BONE	Hand
Foot erosions	12	7	MTP1, MTP2, MTP3, MTP4, MTP5, INTERPHALANGEAL JOINT 1	Foot
PIP JSN	8	5	PIP2, PIP3, PIP4, PIP5	Hand
DIP JSN	8	5	DIP2, DIP3, DIP4, DIP5	Hand

MCP + thumb JSN	12	7	MCP1, MCP2, MCP3, MCP4, MCP5, Hand INTERPHALANGEAL JOINT OF THE HAND
Wrist JSN	12	7	CMC3, CMC4, CMC5, RADIOCARPAL, SCAPHOID- TRAPEZIUM, CAPITATE- NAVICULAR-LUNATE
Foot JSN	12	7	MTP1, MTP2, MTP3, MTP4, MTP5, Foot INTERPHALANGEAL JOINT 1

### **Handling of multiple X-ray readers**

The readings of the x-rays and the scoring will be performed centrally. Two central independent primary radiograph readers, both blinded to treatment arm and radiograph sequence, will analyze the digitized images. In the case that adjudication is needed, the primary independent reviewers will re-read images first. The re-read results will be considered as the final primary read results. Following the re-reads, adjudication will commence if the adjudication is still needed. A third reader (i.e. an adjudicator different from the primary reviewers for a given subject) will make an independent assessment.

Each reader's total score is calculated separately at the patient level for BSL, Follow Up (FU) and Change from BSL as detailed in [Appendix 5-3](#). The statistical analysis will use the mean total score from all three readers, if available, or the mean total score from the two readers otherwise.

### **Handling of rescued/early escape patients data**

Two scenarios might be observed:

Subjects following the original protocol who are non-responder at Week 16 (not achieving a  $\geq 20\%$  improvement from baseline in both TJC and SJC) will have their hands/wrists and feet X-rays taken at Week 16 and no additional X-ray at week 24.

Subjects following the amendment 1 of the protocol who are non-responders at week 16 are expected to have both a week 16 and week 24 X-ray taken.

All subjects (irrespective of the protocol version) who are responder at Week 16 ( $\geq 20\%$  improvement from baseline in both tender and swollen joint counts) will have their hands/wrists and feet X-rays taken at Week 24.

For patients receiving rescue therapy (who meet the criteria for early escape at Week 16) their week 24 X-ray assessment will be treated as missing for placebo treatment and linear extrapolation will be used to impute the value at Week 24.

### **Missing data following imputation and averaging over readers**

Following application of the imputation algorithm during data derivation, there will be no further imputation of data during the analysis, even if there are missing joint scores e.g. at baseline. If BSL or all post- BSL total modified Sharp score/s is/are missing for a subject, the subject will be excluded from the analyses.

## **Health Assessment Questionnaire - Disability Index (HAQ-DI)**

The Health Assessment Questionnaire (HAQ©) was developed by Stanford University and is one of the most widely used measures to assess the long-term influence of chronic disease on a subject's level of functional ability and activity restriction. The disability assessment component of the HAQ (Health Assessment Questionnaire – Disability Index), the HAQ-DI, assesses a subject's level of functional ability and includes questions of fine movements of the upper extremity, locomotor activities of the lower extremity, and activities that involve both upper and lower extremities. There are 20 questions in eight categories of functioning including dressing, rising, eating, walking, hygiene, reach, grip, and usual activities. The stem of each item asks over the past week "Are you able to ..." perform a particular task. Each item is scored on a 4-point scale from 0 to 3, representing normal (normal, no difficulty [0]), some difficulty [1], much difficulty [2], and unable to do [3].

Scoring for the eight functional categories and overall disability index scoring will be performed as follows:

There are eight categories; first score within each category:

- Dressing and Grooming, includes items 1 and 2
- Arising, includes items 3 and 4
- Eating, includes items 5, 6 and 7
- Walking, includes items 8 and 9
- Hygiene, includes items 10, 11, and 12
- Reach, includes items 13 and 14
- Grip, includes items 15, 16 and 17
- Activities, includes items 18, 19, and 20

The score for each category will be the single response within the category with the highest score (greatest difficulty). For example, in the "Eating" category, there are two answers (one for each item). If "Cut your food with a knife or fork" is marked as "3" and "Lift a full cup or glass to your mouth" is marked as "0", then the score for the "Eating" category would be "3" (the response indicating the greatest difficulty within the category).

If a component question is left blank or the response is too ambiguous to assign a score, then the score of that category will be determined by the remaining completed question(s).

However, if **any** "aids or devices" and/or "help from another person" items at the bottom of each page are checked, the category to which they apply will be adjusted upward to "2". If the basic score is **already** "2" or "3", the score remains unchanged. The checking of the items "Aids or devices" and "help from another person" can **only** change a category's score to "2"; they do **not** change the score to a "1" or a "3".

The score for the disability index will be the mean of the eight category scores. If more than two of the categories, or 25%, are missing, scale will not be scored. Otherwise, divide the sum of the categories by the number of answered categories. The higher score indicates greater disability.

Errors occurred during the translation to some languages of the questionnaire in one of the items of the 4-point scale. This could have led to a misinterpretation of the remaining answer options, affecting patients responses to 20 questions. Therefore the answers of the affected languages and software version are flagged. These flagged answers will not be used in any analyses and only be listed with a flag and corresponding footnote.

**HAQ-DI response** is defined by an improvement of at least 0.3 score points compared to baseline.

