9.4.3 Handling of missing values/censoring/discontinuations

Missing data for ACR20 response and other binary efficacy variables (e.g. ACR50, ACR70, HAQ-DI[®] response, etc.) for data up to Week 24 will be handled as follows:

- Subjects who drop out of the trial for any reason will be considered non-responders from the time they drop out through Week 24.
- Subjects who do not have the required data to compute ACR response (i.e. tender and swollen joint counts and at least three of the five ACR core set variables) at BSL and at the specific time point will be classified as non-responders.

Continuous variables (e.g. ACR components, DAS, etc.) will be analyzed using a mixed-effects repeated measures model (MMRM) which is valid under the missing at random (MAR) assumption. For analyses of these parameters, if all post-BSL values are missing then these missing values will not be imputed and this subject will be removed from the analysis of the

[figure not shown]
corresponding variable, i.e. it might be that the number of subjects providing data to an analysis is smaller than the number of subjects in the FAS.

Data collected after Week 24 will generally be presented as 'observed case'; i.e. all available data for each time point will be included in the analyses.

In general, the handling of data for subjects who are rescued at Week 16 will be handled in the following fashion for comparisons with placebo at Week 20 and Week 24:

- For each binary endpoint, a subject will be considered as a non-responder at Week 20/24 for that endpoint if the subject is a non-responder (including missing imputed non-responder) at Week 16. If a subject is a responder at Week 16, the actual value at Week 20/24 will be used (missing is considered as non-responder). This will be done for all treatment regimens in order to minimize bias.
- For continuous endpoints, the goal of the analyses would be to estimate what would have happened if the subjects had stayed on the original treatment. Thus, the data collected after the subject switches to secukinumab will be treated as missing for placebo subjects and will be analyzed using a MMRM which is valid under the missing at random (MAR) assumption. For secukinumab subjects, the actual values will be used in the analysis.

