### **2.6.3 Handling of missing values/censoring/discontinuations**

#### **Missing data**

Missing data for binary efficacy variables for data up to Week 52 will be handled as follows:

- Subjects who drop out of the trial for any reason will be considered non-responders from the time they drop out through Week 52 for active groups or through Week 24 for placebo group.
- Subjects who do not have the required data at baseline and at the specific time point to compute response will be classified as non-responders.

Continuous variables (e.g. ACR20 components) will be analyzed using a mixed-effects repeated measures model (MMRM) which is valid under the missing at random (MAR) assumption. As such, single-point imputation of missing data will not be performed (e.g. LOCF). For analyses of these parameters, if all post-baseline values are missing then these missing values will not be imputed and this subject will be removed from the analysis of the corresponding variable, i.e. it might be that the number of subjects providing data to an analysis is smaller than the number of subjects in the FAS.

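### HAQ answers voided for a translation error are counted as non-response in the binary HAQ-DI response analysis, because the visible text makes no exception to the non-responder rule

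*SAP*

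**What the plan says.** **The fault and its handling.** The HAQ-DI part of SAP 2.12.4.1 states: "Errors occurred during the translation to some languages of the questionnaire in one of the items of the 4-point scale". It describes the consequence as "affecting patients responses to 20 questions", and continues: "Therefore the answers of the affected languages and software version are flagged". The instruction that follows is "These flagged answers will not be used in any analyses and only be listed with a flag and corresponding footnote".

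**Scoring.** The same subsection sets a floor for the index: "If more than two of the categories, or 25%, are missing, scale will not be scored". HAQ-DI response "is defined by an improvement of at least 0.3 score points compared to baseline", so it needs a score at baseline and at the visit.

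**Missing binary data.** Protocol 9.4.3 opens its rule with "Missing data for ACR20 response and other binary efficacy variables (e.g. ACR50, ACR70, HAQ-DI", so HAQ-DI response is named as one of the variables covered. SAP 2.6.3 says: "Subjects who do not have the required data at baseline and at the specific time point to compute response will be classified as non-responders".

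**HAQ-DI change.** The secondary endpoint in the testing hierarchy (H16 to H18) is change from baseline at Week 16. SAP 2.6.2.2 analyses it by MMRM under MAR. SAP 2.6.3 drops a subject with no post-baseline value from such an analysis; it does not count the subject as a failure.

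**ACR.** SAP 2.12.4.1 requires improvement in both joint counts and in three of five further measures, of which HAQ is one. Protocol 9.4.3 keeps a subject evaluable if both joint counts and three or more of the five measures are present.

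**The concern.** Non-responder imputation is usually defended on the ground that leaving the study, or having no assessment, is itself an unfavourable outcome. That argument does not apply here. Whether an answer is flagged depends on the language and software version of the form, so it says nothing about how the subject fared. Counting such a subject as a HAQ-DI failure turns a fault in the form into an apparent lack of effect in every arm.

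The plan also treats the same lost score in two ways: as missing at random for HAQ-DI change and as failure for HAQ-DI response. The two HAQ-DI results could then disagree for a reason unrelated to treatment. What is at stake is the reported HAQ-DI response rates and the differences between arms, and to a much smaller degree the ACR rates. No confirmatory conclusion is at stake.

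**Working it through.** **1. From flag to non-response.** All 20 questions are affected, so all eight categories are missing at a flagged visit. The index allows at most two missing categories, so there is no score. Without a baseline or visit score, response cannot be computed, and the binary rule assigns non-response. Flagging follows language and software version, so it may differ between visits of the same subject. The rule applies at a visit whenever baseline or that visit is flagged.

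**2. Dilution of HAQ-DI response.** Let f be the share of subjects affected at a visit, equal across arms and unrelated to response. Then

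observed rate = (1-f) × p + f × 0 = (1-f) × p, and observed difference = (1-f) × (pA - pP).

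The documents give neither f nor HAQ-DI response rates. With assumed rates of 50% and 30%:

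| f | active | placebo | difference | odds ratio |
|---|---|---|---|---|
| 0 | 50% | 30% | 20 points | 2.33 |
| 10% | 45% | 27% | 18 points | 2.21 |
| 20% | 40% | 24% | 16 points | 2.11 |
| 30% | 35% | 21% | 14 points | 2.03 |

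**3. The plan's own HAQ-DI figure.** SAP section 3 gives about 94% power for HAQ-DI change, with difference 0.17, SD 0.49, 220 vs 330 subjects and two-sided alpha 1.67%. The noncentrality is 0.17 / (0.49 × √(1/220 + 1/330)) = 0.17 / 0.04265 = 3.99, and the noncentral t gives 94.3%, so the figure reproduces. If flagged subjects contribute nothing to this analysis, power is 91.6% at f = 10%, 87.7% at 20% and 82.3% at 30%. At the full 5% level, used if the second family is reached, it is 97.8% with none flagged and 91.4% at 30%. This is a loss of information, not failure imputation, but it is a reason to report f.

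**4. ACR.** With HAQ unavailable, a flagged subject stays evaluable but must improve in three of the four remaining measures. I modelled the seven ACR components as equally correlated normal variables (assumed correlation 0.3, 0.5 or 0.7; 200,000 draws). The model was calibrated to the SAP's 51% and 15% under three of five, then rescored under three of four.

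| correlation | active, flagged | placebo, flagged | odds ratio |
|---|---|---|---|
| 0.3 | 45.5% | 11.6% | 6.4 |
| 0.5 | 47.0% | 12.5% | 6.2 |
| 0.7 | 48.1% | 13.3% | 6.1 |

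Unflagged, the odds ratio is (0.51/0.49) / (0.15/0.85) = 5.9. With 10% to 30% flagged, whole-arm ACR20 is 49.3% to 50.7% on active and 14.0% to 14.8% on placebo. Power at 1.67% remains above 99%. ACR50 power, from 35% vs 7%, also stays above 99% at 30% flagged.

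**The case against.** The strongest reply is that little of consequence depends on this. Binary HAQ-DI response is not in the secondary endpoint list of SAP 2.6.1. Flagging does not depend on treatment, so randomisation balances it on average and it does not inflate type I error. The plan follows the protocol's stated rule for HAQ-DI response, and excluding subject-visits departs from the FAS. SAP 2.5.4 and 2.7 are not visible in the public copy, and a specific rule could sit there. All of this stands. It makes the point minor, but it does not justify counting a voided form as a treatment failure.

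Several stronger readings are tempting, and the documents do not support them:

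- *Flagged subjects become failures on the tested HAQ-DI endpoint.* They do not. H16 to H18 test change from baseline by MMRM.
- *The non-responder rule raises the ACR hurdle.* It does not, since a subject missing only HAQ remains evaluable. The three-of-four requirement comes from the ACR definition and would apply to any missing measure.
- *ACR has no remedy.* SAP 4.2.3 already sets out multiple imputation by component, with ACR response calculated on the completed data.
- *An affected subject fails at every visit.* That would follow from a flagged baseline, but not from a flag at one later visit.
- *The sponsor made the error.* The SAP says only that errors arose in translation.

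**Conclusion.** The concern holds for binary HAQ-DI response and is minor. On the visible text, a flagged baseline or visit HAQ is counted as non-response, which shrinks response rates and their differences by the factor (1-f). The size cannot be fixed because f is not reported, and the illustration rests on assumed response rates and on f being equal across arms. The effect is dilution towards no difference.

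The ACR effect is separate and small. Among flagged subjects, response falls by about 3 to 6 points on active and 2 to 3 on placebo, under the assumed correlations. The primary comparison keeps its power, and its odds ratio is not attenuated. It would be wrong to infer that the primary result or the HAQ-DI hypotheses in the hierarchy are compromised by failure imputation.

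**What to change.** 1. For binary HAQ-DI response, exclude from numerator and denominator every subject-visit at which the baseline or visit HAQ was flagged for the translation error. Keep non-responder imputation for all other missing data.
2. Record this in the SAP as a departure from Protocol 9.4.3, with the reason.
3. Tabulate flagged subjects by arm and visit, so that f and its balance can be seen. Randomisation is stratified only by TNF status, so balance by language is expected but not enforced.
4. For ACR, confirm that flagged HAQ values enter the component-level multiple imputation of SAP 4.2.3 as missing. No further ACR analysis is needed.
5. If SAP 2.5.4 or 2.7 already holds a rule for flagged answers, a cross-reference from SAP 2.12.4.1 is enough.

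The cost is a few lines of SAP text, one table and a smaller denominator for HAQ-DI response.
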